3.1 Randomisation

Randomisation will occur within 120 days of completion of standard therapy. After informed consent is signed and subject's eligibility is confirmed, the subject can be randomised in a 1:1

allocation ratio (Aspirin group: 200 mg Aspirin once a day for 3 years or placebo group: 200 mg matching placebo once a day for 3 years), stratified by

- Study centre
- Tumour type (Dukes C colon, high risk Dukes B colon cancer, or rectal cancer sub-groups) and
- Type of adjuvant chemotherapy received (exposed/ not exposed to Oxaliplatin)

All randomisations will be done via direct web randomisation. Authorised study centre personnel will randomise the subjects via a password-protected internet web site provided by Singapore Clinical Research Institute.

3.2 Treatment Schedule

A total of 1587 subjects will be randomised from multinational centres. After randomisation, subject will have 3-monthly assessments for 3 years (month 3 to month 36) followed by 6-monthly assessments for additional 2 years (month 42 to month 60). Subjects who consent to continue information collection after month 60 will have vital data captured via review of medical records or phone call.

The study drug, oral Aspirin 200 mg/ placebo 200 mg once a day, should begin immediately but no later than 2 weeks of randomisation. The study drug will be stopped immediately if there is a disease recurrence confirmed by CT, histology or cytology. In the event of SAE related to the study drug, the study drug will be stopped immediately.

The investigator has the right to discontinue study treatment if he/she feels that it is in the best interests of the subject or due to safety concerns. The reasons for treatment discontinuation will be documented. All subjects, including subjects who discontinued from study treatment, will continue to be followed for 5 years after randomisation, unless the subject is lost to follow up, died or withdrew consent.

3.3

3.4 Assessment Schedule

The table below gives an overview of study follow-up and assessment schedule. Phone assessments are allowed at alternate 3-monthly assessments should the subject is unable to return for a follow-up. In the first 3 years, subjects with early treatment discontinuation but without recurrence will only continue with 3-monthly visit. Haemoglobin assessment will not be required for these subjects. In the first 3 years, subjects with recurrence will be assessed at 6-monthly intervals in the clinic or via phone assessments if they are unable to return for 3-monthly clinic follow up. Haemoglobin, CEA and concomitant medication assessments are not required after recurrence. In the last 2 years, subjects with recurrence may have their 6-monthly assessments via phone should they are unable to return for clinical follow up. CEA assessments are not part of these subjects' 6-monthly assessments.

Assessments	Screening*	Baseline	Follow-up month (+/- 1 month)			Follow-up month (+/- 1 month) after recurrence	Follow-up month (+/- 1 month) after early treatment discontinuation but without recurrence	Post month (
			3-monthly in first 3 years		6-monthly in last 2 years			
			3, 9, 15, 21, 27, 33	6, 12, 18, 24, 30, 36				
Written informed consent	x							
Demography, colorectal cancer surgery and tumour history, risk factors, medical history, family history of colorectal cancer		x			3-monthly followed by 6 monthly 3 to 60	3-monthly 3 to 36		
Record surgical measurements (for rectal cancer only) and synchronous tumours characteristics		x						
Adjuvant therapy		x						
Vital signs (body weight, height, blood								

pressure), ECOG																									
Haemoglobin				x											x										
Laboratory investigations (platelet count, creatinine, serum bilirubin, AST, ALT)			x (Within 8 weeks prior to randomisation)																						
CEA			x (Within 8 weeks prior to randomisation)												x										
Imaging of abdomen (CT or CT colonogram or MRI or PET or Ultrasound)			x (Within 16 months prior to randomisation)																						
Radiological examination of the chest (including but not restricted to chest X-ray, CT thorax or PET scan)			x (Within 16 months prior to randomisation)																						
Colonoscopy / CT colonogram			x (Within 16 months prior to randomisation)																						
Protocol treatment compliance															x										
Adverse event and serious adverse event															x										
Death															x										
Medical events															x										
Concomitant NSAIDs															x										
Concomitant treatment/ medication															x										
Recurrence, salvage chemotherapy															x										
															x										
															x										
															x										
															x										
															x										
															x										

3.5 Sample Size Calculation

Initial sample size calculation (before start of the study)

The initial total trial size was 2660 subjects, with 1330 randomised to Aspirin group and 1330 randomised to Placebo group. In the sub-groups, there should be at least 2000 high risk Dukes B or Dukes C colon cancer patients, others are rectal cancer patients.

It was assumed that 3-year DFS rate for Dukes B colon cancer, Dukes C colon cancer and rectal cancer are 65% after standard adjuvant chemotherapy; and the attrition rate is 5%. The total trial size (2660) would be sufficient to detect an absolute difference of 6% in DFS rate between the two groups amongst all subjects, with a two-sided log-rank test of 5% type I error and 90% power. For the main sub-group analysis, the 3-year DFS rate for colon cancer patients is assumed to be 65% under standard care, which is similar to the entire group as a whole, the size of colon cancer group (2000) would be sufficient to detect a 6% absolute difference in DFS rate for colon cancer between the two groups, with a two-sided logrank test of 5% type I error and 80% power.

Subsequent sample size calculation (20 March 2013)

Based on recent studies of Aspirin in colorectal cancer patients, with a reported hazard ratio (HR) or risk ratio ranging from 0.67 to 0.77, we assumed a HR of 0.72 for DFS between Aspirin and the placebo group. The corresponding absolute difference in DFS rate between the two groups was about 8.5% instead of 6% for a 3-year DFS rate of 65% in the placebo group. To detect a HR of 0.72, a total of 300 recurrences (or deaths if occur without recurrence) is required for a two-sided logrank test of 5% type I error and 80% power. This translates to a total sample size of 1200 subjects if the DFS rate is 65% in the placebo group and attrition rate is 15%.

Latest sample size calculation (9 May 2018)

A recent review of pooled trial interim data (i.e. not stratified by treatment group), after enrolment of at least 1140 subjects and 3 years of follow-up being completed in 430 subjects,

revealed a pooled DFS rate of 79% at 5-year. With a total sample size of 1200, an estimate of only 240 recurrences would be observed, a shortfall of 60 recurrences to maintain the study power at 80%. To observe 300 recurrences (or deaths) at the end of study, a sample size of 1587 subjects would be required with attrition rate reduced from 15% to 10%, while the rest remains unchanged.

4 STATISTICAL ANALYSIS

4.1 General

Continuous variables will be summarised using descriptive statistics, i.e., mean, standard deviation, median, interquartile range (IQR), minimum and maximum. Categorical variables will be summarised by frequency and percentage. All statistical significance tests and confidence intervals are two-sided. A p-value <0.05 is considered statistically significant. All confidence intervals (CIs) are at 95% level. All statistical analyses will be conducted using SAS version 9.2 or higher (Statistical Analysis System software, SAS Institute, North Carolina, USA).

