2. STUDY OBJECTIVE

To assess the effectiveness of Aspirin against placebo control in patients with dukes C or high risk dukes B colorectal cancer in terms of Disease Free Survival (DFS) and Overall Survival (OS)

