2 STUDY OBJECTIVES

Primary objective

Null hypothesis: Among subjects with Dukes C or high risk Dukes B colorectal cancer, Disease Free Survival (DFS) between those randomised to Aspirin and those randomised to placebo control is equal.

Alternative hypothesis: Among subjects with Dukes C or high risk Dukes B colorectal cancer, DFS between those randomised to Aspirin and those randomised to placebo is not equal.

Primary objective: To compare DFS between the group randomised to Aspirin with the group randomised to placebo control in subjects with Dukes C or high risk Dukes B colorectal cancer.

Secondary objectives

1. To compare the DFS between the group randomised to Aspirin with the group randomised to placebo control in subjects with high risk Dukes B and Dukes C colon cancer.
2. To compare the overall survival (OS) between the group randomised to Aspirin with the group randomised to placebo control in subjects with Dukes C or high risk Dukes B colorectal cancer.

Exploratory objectives

1. To compare the DFS and OS between the group randomised to Aspirin with the group randomised to placebo control in subjects with Dukes C or high risk Dukes B colorectal within the following subgroups:
 - a. Baseline variables
 - i. Country.

Countries with small sample size (less than 25) will be pooled under 'Others' or with countries with similar ethnic population.

- ii. Resected high risk Dukes B colon cancer, Dukes C colon cancer, colon cancer and rectal cancer.
- iii. Exposed to Oxaliplatin, not exposed to Oxaliplatin.
- iv. Ethnicity (East Asian, South Asian, Caucasian and Others).
- v. Type of surgery (laparoscopic surgery, open surgery).
- vi. Chemotherapy duration (<3 months, 3-6 months, >6 months).
- vii. Age group (<70, ≥70).

b. Translational variables

- i. Compliant subjects, non-compliant subjects.

Compliant subject is defined as an individual who is on the study drug for at least 70% of days in first year from randomisation or up to treatment discontinuation or recurrence, whichever is earlier.

- ii. Duration of exposure to study drug (<1 year, 1-2 years, >2 years).

The duration of exposure to study drug during the treatment period is defined as the number of days from the first dose to the last dose excluding days of interruptions, i.e. "duration of exposure" = "last dosing date" – "first dosing date" – "days off medication" + "1 day".

- iii. PIK3CA mutations (mutant PIK3CA, wild-type PIK3CA)

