4.6 Time-to-event Endpoints

For primary outcome of DFS, survival curves will be constructed using the Kaplan-Meier method. Product-limit estimates of 3- and 5-year survival rates will be calculated. Median survival times will also be reported. The complementary log-log transformation will be used for deriving the median survival times corresponding 95% CIs. The primary analysis will be a mITT analysis which uses stratified logrank test adjusting for trial stratification factor

(centre pooled by country (categorical), type of tumour (Dukes C colon vs. high risk Dukes B colon vs. rectal; categorical) and type of adjuvant chemotherapy (exposed vs. not exposed to Oxaliplatin; categorical)) to generate p-value comparing the treatment groups, followed by multivariate Cox proportional hazard (PH) regression model to estimate adjusted HR and its corresponding 95% CI. The multivariate Cox PH regression model will also include the trial stratification factors used in the stratified logrank test as covariates. Additional covariates such as time from surgery to first chemotherapy in days (continuous), type of surgery (laparoscopic surgery vs. open surgery; categorical), chemotherapy duration (<3 months vs. 3-6 months vs. >6 months; categorical) and age group (<70 vs. ≥ 70 years old; categorical) will be added as part of sensitivity analysis. The CI of the HR will be based on profile-likelihood. Firth's correction may be used if monotone likelihood phenomenon is observed. Unadjusted HR and p-value from non-stratified logrank test will also be reported as supplementary results.

As part of secondary objective, the same analysis on DFS will be repeated for sub-population of colon cancer except that the covariate, type of tumour, will consist of only two categories: Dukes C colon vs. high risk Dukes B colon.

The secondary outcome of OS will be analysed in a similar manner as the primary endpoint, except that repeated analysis on colon cancer sub-population will not be done.

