For all subgroup analyses of DFS and OS by different countries, tumour types (high risk Dukes B colon, Dukes C colon, colon, rectal), adjuvant chemotherapy types (exposed to Oxaplatin, not exposed to Oxaliplatin), ethnic groups (East Asian, South Asian, Caucasian, Others), type of surgery (laparoscopic surgery, open surgery), chemotherapy duration (<3 months, 3-6 months, >6 months), age group (<70, ≥ 70), levels of compliance (<70%, $\geq 70\%$), duration of exposure to drug (<1 year, 1-2 years, >2 years), PIK3CA mutations (mutant PIK3CA, wild-type PIK3CA) and COX-2 expression (positive for COX-2 overexpression, negative for COX-2 overexpression), tests for interactions between treatment group and the subgroup variable of interest will be conducted first. As the subgroups under tumour types are not mutually exclusive, the test for interaction will be based on the original mutually

exclusive groups. Results of subgroup analyses will be presented in forest plots. Subgroup analyses will be considered as exploratory.

Appropriateness of Cox PH regression model will be checked using graphical method of log-log survival curves for treatment indicator and each covariate. Continuous covariate will be dichotomised at mean value to check for the PH assumption. PH assumption will be considered not satisfied if there is strong evidence of non-parallelism in the log-log survival curves. Should there be at least one covariate not satisfying the PH assumption, “no-interaction” (i.e. estimated coefficients not varying by stratum) stratified Cox regression model will be used instead. The model will be stratified by strata formed after combining categories of all covariates which did not satisfy the PH assumption. Covariate(s) which satisfies the PH assumption will remain included in the stratified model. If the treatment indicator is found to not satisfy the PH assumption, time-varying HR will be obtained by partitioning the follow-up time into 1-year intervals.

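### The SAP lets colon-cancer DFS and OS each be called statistically significant at p<0.05 with no gate on the primary DFS test, no testing order and no alpha split

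*SAP*

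**What the plan says.** SAP 4.1 covers all testing in two sentences: "All statistical significance tests and confidence intervals are two-sided", and "A p-value <0.05 is considered statistically significant". Neither is limited to the primary endpoint.

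SAP section 2 has three tiers. The primary objective is DFS in all subjects, with a stated null and alternative hypothesis. There are two secondary objectives: colon-cancer DFS ("To compare the DFS between the group randomised to Aspirin with the group randomised to placebo control in subjects with high risk Dukes B"; the sentence goes on to include the Dukes C colon group) and OS. A separate list holds the exploratory objectives.

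SAP 4.6 defines the primary test: "The primary analysis will be a mITT analysis which uses stratified logrank test adjusting for trial stratification factor". For the first secondary it says "As part of secondary objective, the same analysis on DFS will be repeated for sub-population of colon cancer", with the tumour-type covariate reduced to two levels. For the second it says "The secondary outcome of OS will be analysed in a similar manner as the primary endpoint", without a repeat in colon cancer. The exploratory label is given elsewhere: "Subgroup analyses will be considered as exploratory". The competing-risk analysis is exploratory through section 2.

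No multiplicity procedure appears in SAP 4.1 to 4.9 or in protocol 12.1 to 12.3. SAP mock-up Table 7 prints hazard ratios and p-values for OS and colon DFS in the same format as for the primary.

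Colon DFS has three statuses. Protocol section 3 lists it under the primary endpoints, SAP section 2 makes it a secondary objective, and colon cancer is also an entry in the exploratory tumour-type subgroups.

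**The concern.** A plan that names one primary hypothesis should also say what a small p-value on a secondary endpoint means when the primary fails. This one does not. Followed as written, SAP 4.1 allows OS or colon DFS to be reported as statistically significant after a null result for all-subject DFS.

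Both are results that readers would take seriously. Protocol section 2 names DFS and OS together as the measures of effectiveness. Colon DFS is a primary endpoint in the protocol, and the superseded 2660-patient design gave the colon group its own test at 5% type I error and 80% power. Because colon DFS appears at more than one tier, its standing could also be argued after the results are known.

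**Working it through.** **The plan's own figure.** SAP 3.5 requires 300 DFS events for HR 0.72, two-sided 5%, 80% power and 1:1 allocation.

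- Schoenfeld: 4 × (1.960 + 0.842)² / (ln 0.72)² = 290.9, so 291 events.
- Freedman: (1.72/0.28)² × (1.960 + 0.842)² = 296.2, so 297 events.
- Power at 300 events: Φ(√300/2 × 0.3285 − 1.960) = 0.812.
- Sample size: 300 / (0.21 × 0.90) = 1587, from the pooled 79% five-year DFS and 10% attrition.

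The sizing reproduces, and it covers one DFS test at 5%.

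**Three tests at 5% each.** The tests are all-subject DFS, colon DFS and OS, each counted once as the mITT stratified log-rank test. Other p-values and the interim looks are not counted. All three nulls are taken as true.

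Bounds that need no correlation: 1 − 0.95³ = 14.3% if independent, and 3 × 5% = 15% by Bonferroni. Neither is realistic, because colon DFS is nested in all-subject DFS and OS shares events with it.

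With correlation, the three statistics are treated as trivariate normal with critical value ±1.96:

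- corr(all DFS, colon DFS) = √f, where f is the colon share of DFS events
- corr(all DFS, OS) = r
- corr(colon DFS, OS) = r√f

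Neither f nor r is in the documents. The only guide to f is the superseded minimum of 2000 colon patients in 2660, or 75%, which is a share of patients rather than events. I took f from 50% to 85% and r from 0.5 to 0.9.

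Each cell gives the chance of at least one p<0.05 among the three tests, then the chance that a secondary has p<0.05 while the primary does not. The second is the first minus 5%, because the primary rejects in 5% of null trials.

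| Colon share f | r = 0.5 | r = 0.7 | r = 0.9 |
|---|---|---|---|
| 50% | 12.2% / 7.2% | 11.4% / 6.4% | 10.1% / 5.1% |
| 75% | 11.2% / 6.2% | 10.4% / 5.4% | 9.1% / 4.1% |
| 85% | 10.7% / 5.7% | 9.9% / 4.9% | 8.5% / 3.5% |

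The two DFS tests alone, with no assumption about OS, give 7.3% at f = 75%.

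**With a gate.** If the secondaries are tested only after the primary has p<0.05, then under the global null a false claim requires a false primary rejection, so the family rate is 5%. If the primary effect is real, a fixed sequence or Holm at 5% holds the error for the two secondaries at 5%.

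**The case against.** The strongest reply is that the SAP already has a hierarchy. Section 2 states hypotheses for all-subject DFS only, the current sizing is for that one test, and OS is secondary in both documents. On this view the 4.1 sentence is general boilerplate, and nothing says that a secondary result can stand as trial success. Treating the three tests as one family is a reviewer's choice, and testing regardless of the primary result is inferred from silence.

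Much of this stands, and it rules out several stronger readings:

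- A reader might infer that the primary test's error is inflated. In this calculation it is not; it stays at 5%.
- A reader might infer that the plan breaches its own 5%. That 5% is a per-test level, and no family-wise rate is stated.
- A reader might quote 14%. That is the independence figure. A correlation of 0.3 between all-subject and colon DFS would imply a colon event share of 0.3² = 9%, and 0.5 would imply 25%; neither fits the 75% in the earlier design.
- A reader might take protocol section 2 to mean that OS alone could meet the objective. The endpoint lists rank OS as secondary.

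The reply does not close the gap. The secondary label says which result comes first, not what may be claimed when that result is negative. SAP 4.1 answers with p<0.05 for everything, and 4.6 withholds confirmatory standing only from the subgroup analyses.

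**Conclusion.** The point holds as an omission in the rules for the secondary endpoints. As written, either colon DFS or OS can be labelled statistically significant after a failed primary. With no true effect on any of the three, at least one such label arises in about 9-12% of trials (about 10% at a 75% colon share and DFS-OS correlation 0.7). A secondary-only label arises in about 4-6% at a 75% share, and about 4-7% over shares of 50-85%. These sizes rest on the assumed event share and correlations; no combination tried brings the family rate down to 5%.

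This should be corrected before unblinded final results are seen. It does not undermine the primary analysis.

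**What to change.** In SAP 4.1 and 4.6, limit the p<0.05 rule to the primary test and a gated secondary family, for example:

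> Colon-cancer DFS and OS will be tested for statistical significance only if the primary stratified log-rank test of all-subject DFS has p<0.05. They will then be tested [in the fixed order ..., each at two-sided 5%] [by Holm's procedure at a two-sided family level of 5%]. Otherwise their p-values are nominal and the results exploratory.

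A fixed sequence and Holm are both valid; one must be chosen in advance.

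Two further changes belong in the same edit:

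- Reconcile the status of colon DFS between protocol section 3 and SAP section 2. The gate above presumes the SAP's single primary. If colon DFS is to remain a primary endpoint, alpha must be allocated between the two DFS tests instead.
- Keep the colon entry in the exploratory subgroup list. SAP 4.6 does not repeat OS in colon cancer as a secondary analysis, so this entry is the only planned colon OS analysis. Mark its DFS forest-plot row as a display of the secondary analysis.

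The primary test keeps its full 5%, so its power, the 300 events and the 1587 subjects are unaffected. The cost falls on the secondaries. A favourable OS or colon result after a non-significant primary becomes hypothesis-generating. Under Holm, the smaller secondary p-value must be below 0.025; under a fixed sequence, the second comparison depends on the first. Reconciling colon DFS may also need a protocol clarification, so the work may extend beyond the SAP.

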4.2 Analysis Populations

All efficacy analyses will be carried out on modified intention-to-treat (mITT) basis, i.e., all subjects who signed the informed consent form for the study enrolment and commenced study treatment after the randomisation are to be analysed as randomised.

As part of sensitivity analysis, efficacy analysis on per-protocol basis will also be performed. Per-protocol analysis consists of subjects included in the mITT population after excluding those with major protocol deviation and those who were compliant <70% of the days in the first year from randomisation. Compliance has been defined in section 2.

Subjects included in safety data analysis are those who received at least one dose of the study treatment drug. These subjects will be grouped and analysed as actually treated.

The number of subjects screened, randomised to the study treatment, completing each subsequent study period including up to 3-year treatment and 5-year follow-up will be summarised in a CONSORT flow chart.

